#### **7.7.1 Criteria for Premature Patient Withdrawal**

Patients **may** voluntarily withdraw from the study or be dropped from it at the discretion of the investigator at any time. Patients may be withdrawn from the study if any of the following occur: pregnancy; discovery of patient ineligibility; errors in treatment compliance [study drug, other prescribed or non-prescribed medications]; missed/unscheduled/off-schedule/incomplete/incorrect assessments.

#### **7.7.2 Follow-up for Toxicities**

Patients whose treatment is interrupted or permanently discontinued due to an adverse event or abnormal laboratory value must be followed at least once a week for 4 weeks, and subsequently at 4-week intervals, until resolution or stabilization of the event, whichever comes first. If a patient requires a dose delay of > 14 days from the intended day of the next scheduled dose, then the patient must be discontinued from the study. However, the patient will continue to be followed for toxicity as previously described. All patients will be followed for adverse events and serious adverse events for 30 days following the last dose of dovitinib.

### **7.8 Replacement Policy**

Patients prematurely withdrawn within the first 3 months of therapy and prior to the first post-therapy cystoscopy with urine cytology and TURBT will be replaced. Patients prematurely withdrawn after their first post-therapy cystoscopy with urine cytology and TURBT will not be replaced.

### **7.9 Follow up Period**

All patients must have safety evaluations for 30 days or 5 half-lives (whichever is longer) after the last dose of study treatment. All patients will be followed for tumor relapse status until tumor relapse is noted or for 12 months beyond last dose of study treatment in patients who stopped dovitinib prior to disease relapse.

Patients lost to follow up should be recorded as such on the eCRF. For patients who are lost to follow-up, the investigator should show "due diligence" by documenting in the source documents steps taken to contact the patient, e.g., dates of telephone calls, registered letters, etc.

## 7.10 Assessment Types

### 7.10.1 Demographics

At baseline, demographic and baseline characteristic data will be collected from all patients. See section 7.5 for details.

### 7.10.2 Diagnosis and Extent of Cancer

#### 7.10.2.1 Tumor Stage

Bladder tumor stage will be defined according to the American Joint Commission on Cancer (AJCC) Staging system for bladder tumors (Edge SB et al., 2010). T-stage classifications include:

Tx – Primary tumor cannot be assessed

T0 – no evidence of primary tumor

Ta – Noninvasive papillary carcinoma which does not invade into the lamina propria

Tis – Carcinoma in situ

T1 – Tumor invades into the lamina propria but not into the muscularis propria

T2a – Tumor invades into the inner half of the muscularis propria

T2b – Tumor invades into the outer half of the muscularis propria

T3a – Tumor microscopically invades the perivesical tissue

T3b – Tumor macroscopically invades the perivesical tissue

T4a – Tumor invades the prostatic stroma, uterus, or vagina

T4b – Tumor invades into the pelvic wall, or abdominal wall

#### 7.10.2.2 Lymph Node Stage

Bladder lymph node stage will be defined according to the American Joint Commission on Cancer (AJCC) Staging system for bladder tumors.(Edge SB et al., 2010) N-stage classifications include:

Nx – Lymph nodes cannot be assessed

N0 – no lymph node metastasis

N1 – Single regional lymph node metastasis in the true pelvis (hypogastric, obturator, external iliac, or presacral lymph node)

N2 – Multiple regional lymph node metastases in the true pelvis (hypogastric, obturator, external iliac, or presacral lymph nodes)

N3 – Lymph node metastases to the common iliac lymph nodes

### **7.10.2.3 Metastases Stage**

Bladder metastasis stage will be defined according to the American Joint Commission on Cancer (AJCC) Staging system for bladder tumors (Edge SB et al., 2010). M-stage classifications include:

M0 – No distant metastasis

M1 – Distant metastasis

### **7.10.3 Prior Anti-neoplastic Therapy**

At baseline, the following prior anti-neoplastic therapy characteristic data will be collected from all patients:

- Number of prior intravesical BCG courses (i.e. BCG x 2 courses → mitomycin C x 1 course → gemcitabine x 1 course = 2 prior BCG courses)
- Number of prior intravesical courses of any type (i.e. BCG x 2 courses → mitomycin C x 1 course → gemcitabine x 1 course = 4 prior intravesical courses)
- Number and name of prior intravesical agents received (i.e. BCG x 2 courses → mitomycin C x 1 course → gemcitabine x 1 course = 3 prior agents)
- Date of last intravesical therapy of any kind
- Date of last intravesical BCG therapy

### **7.10.4 Vital Signs**

At baseline and subsequent study visits, the following vital signs data will be collected from all patients:

- Temperature (°C)
- Heart rate (beats per minute)
- Systolic blood pressure (mmHg)
- Diastolic blood pressure (mmHg)
- Respiratory rate (breaths per minute)
- Height (cm) [only recorded at baseline]
- Weight (kg)

### **7.10.5 ECOG Performance Status**

At baseline and subsequent study visits, the Eastern Cooperative Oncology Group (ECOG) performance status (PS) data will be collected from all patients. The ECOG PS values are defined as follows:

- ECOG 0 – Fully active, able to carry on all pre-disease performance without restriction
- ECOG 1 – Restricted in physically strenuous activity but ambulatory and able to carry out work of a light or sedentary nature, e.g., light house work, office work

- ECOG 2 – Ambulatory and capable of all self-care but unable to carry out any work activities. Up and about more than 50% of waking hours
- ECOG 3 – Capable of only limited self-care, confined to bed or chair more than 50% of waking hours
- ECOG 4 – Completely disabled. Cannot carry on any self-care. Totally confined to bed or chair
- ECOG 5 – Dead

#### **7.10.6 FGFR1, FGFR2, FGFR3, VEGFR1, VEGFR2, and VEGFR3 Mutation, Over-expression, and Pathway Analyses**

##### **7.10.6.1 FGFR3 Mutation Status**

Somatic FGFR3 mutations (see Table 1-2) in exons 7, 10, and 15 will be assessed in FFPE tumor tissues by massively parallel sequencing analysis utilizing the Ion Torrent Personal Genome Machine (PGM) and performed in the CLIA-certified Molecular Pathology and Translational Research Laboratory at the Dartmouth Hitchcock Medical Center.

Unstained slides from the patients' TURBT sample that was obtained within 42 days of registration will be submitted to two different laboratories prior to registration to determine FGFR3 mutation status and over-expression status. The laboratories will directly notify the site within 5-7 days, the results of the testing. In cases where multiple biopsies were obtained, the site pathologist is asked to send slides from the biopsy with the highest grade and the greatest volume of tumor present within the biopsy sample. Consider the biopsy results depicted below:

Biopsy sample	Location	Diagnosis	Tumor volume
#1	Dome	Ta low-grade UC	Tiny
#2	Rt Lateral wall	T1 high-grade UC + CIS	Moderate
#3	Left Lateral wall	CIS	Small
#4	Posterior wall	T1 high-grade UC + CIS	Large

In the example above, the site pathologist would be asked to send slides from biopsy #4 from the posterior bladder wall.

Consider the biopsy results below:

Biopsy sample	Location	Diagnosis	Tumor volume
#1	Dome	Ta low-grade UC	Tiny
#2	Rt Lateral wall	CIS	Moderate
#3	Left Lateral wall	CIS	Large
#4	Posterior wall	No malignancy	Large

In the example above, the site pathologist would be asked to send slides from biopsy #3 from the left lateral bladder wall.

Consider the biopsy results below:

Biopsy sample	Location	Diagnosis	Tumor volume
#1	Dome	Ta low-grade UC	Tiny
#2	Rt Lateral wall	T1 high-grade UC	Moderate
#3	Left Lateral wall	CIS	Moderate
#4	Posterior wall	No malignancy	Large

In the example above where there is the presence of both T1 high-grade UC and CIS residing in separate samples, the site pathologist would be asked to send slides from both biopsy #2 from the rt lateral bladder wall and biopsy #3 from the left lateral bladder wall.

Refer to SPM for detailed collection, labeling and shipping guidelines. Upon receipt in the laboratory, each slide will be visually inspected for any signs of damage during shipment. One H&E stained slide will be reviewed under light microscope to assess percent tumor cell content. A minimum of 40% tumor cell content is required in the entire tissue section; otherwise, macrodissection will be performed to ensure maximum tumor cell content.

DNA will be isolated utilizing a standard commercially available extraction kit (i.e. Qiagen PureGene) according to manufacturer specifications. FGFR3 mutational status will be determined by DNA sequencing of all coding exons including exons 7, 10, and 15. Upon completion of testing, the presence/absence of an FGFR3 mutation (see Table 1-2) will be communicated to the treating site via email and /or facsimile.

A whole blood sample will be collected at cycle 1 day 1.

DNA from PBMC's will be extracted using a standard commercially available DNA extraction kit (i.e. Qiagen DNeasy™). FGFR3 single nucleotide polymorphisms (SNPs) in PBMC's will be analyzed by commercially validated probes. Refer to SPM for collection and shipping guidelines.

#### **7.10.6.2 FGFR3 Overexpression Status**

Presence of FGFR3 over-expression within tumor tissue will be assessed at study entry by the IUSCC's IHC Core. The IHC antibody used to determine FGFR3 over-expression is commercially available from Novus Biologicals.

Refer to SPM for collection, labeling and shipping guidelines.

Presence of FGFR3 over-expression within tumor tissue will be assessed and interpreted by two separate pathologists. Brain, kidney, and testes are the recommended positive controls. Non specific immune serum will be used as the negative control. Staining intensity will be graded 0, +1, +2, +3 and  $\geq +1$  brown staining in the tissues defines positivity. Up to 3 pieces of tissue are to be analyzed at 3 to 5 high power fields if available.

Upon completion of testing, the presence/absence of FGFR3 over-expression will be communicated to the treating site within 5-7 days.

#### **7.10.6.3 FGFR1 and FGFR2 Mutation Status**

FGFR1 and FGFR2 single nucleotide polymorphisms (SNPs) in PBMC DNA extracted as described in 7.10.6.1 will be analyzed utilizing commercially validated probes. In cases of scant PBMC DNA availability, FGFR3 analyses will take priority over FGFR1 and FGFR2 analyses. Refer to SPM for collection and shipping guidelines.

#### **7.10.6.4 VEGFR1, VEGFR2, and VEGFR3 Mutation Status**

A whole blood sample will be collected at cycle 1 day 1.

DNA from PBMC's will be extracted using a standard commercially available DNA extraction kit (i.e. Qiagen DNeasy™). VEGFR1, VEGFR2, and VEGFR3 single nucleotide polymorphisms (SNPs) in PBMC's will be analyzed by commercially validated probes. Refer to SPM for collection and shipping guidelines.

#### **7.10.6.5 VEGFR Over-expression Status**

Presence of VEGFR1, VEGFR2, and VEGFR3 overexpression within tumor tissue will be assessed by the IUSCC's IHC Core.

Presence of VEGFR1, VEGFR2, and VEGFR3 over-expression within tumor tissue will be assessed and interpreted by standard immunohistochemistry analysis with appropriate controls. Refer to SPM for collection and shipping guidelines.

#### **7.10.6.6 FGFR and VEGFR Pathway Signaling Analyses**

Assessment of the effect of dovitinib on FGFR and VEGFR pathway signaling will be assessed by the IUSCC IHC Core through analysis of pre- and post-treatment TURBT specimens.

All samples will be analyzed for FGFR3, pFGFR3, VEGFR2, pVEGFR2, FRS2, pFRS2, ERK, pERK by standard immunohistochemistry analysis with appropriate controls. Where additional tissue is available, analysis of additional FGFR/VEGFR pathway markers will also be performed. Refer to SPM for collection and shipping guidelines.

### **7.10.7 Cystoscopy, TURBT, and Urine Cytology Evaluations**

#### **7.10.7.1 Cystoscopy and TURBT**

All patients must have an adequate staging cystoscopy and TURBT performed within 42 days prior to study registration. In order to be considered adequate, the muscularis propria portion of the bladder wall must be present within at least one of the TURBT biopsies. All patients will be re-evaluated for response by standard of care cystoscopy every 3 months  $\pm$  7 days (e.g. 3 month, 6 month, 9 month, 12 month) during the first year of follow-up. All patients will be re-evaluated for response by standard of care TURBT/biopsy every 3 months (e.g. 3 month, 6 month)  $\pm$  7 days during the first 6 months of follow-up. At each of the follow-up TURBT/biopsy evaluations, biopsy tissue should be obtained from each of the following areas to ensure uniform disease evaluation and tissue acquisition:

1. All previously documented baseline tumor sites

2. Bladder dome
3. Anterior bladder wall
4. Left lateral bladder wall
5. Right lateral bladder wall
6. Bladder trigone
7. Any additional new suspicious bladder areas

In the absence of recurrence at 1-year from study registration, cystoscopic surveillance and TURBT/biopsies are at the treating physician's discretion.

**NOTE:** Patients with residual non-invasive UC tumors with no component of carcinoma in situ (i.e. Ta, T1) at 3-month cystoscopy and TURBT are not considered relapses and will be permitted to continue on dovitinib therapy. If the subsequent 6-month cystoscopy, TURBT, and urine cytology shows no evidence of any remaining urothelial carcinoma in such patients, they will be considered a complete response. Patients with any component of carcinoma in situ (CIS) at 3-month cystoscopy/TURBT will be considered relapses and will not continue on dovitinib therapy. Any non-invasive UC tumors (i.e. Ta, T1, Tis) at the 6-month or any subsequent cystoscopy/TURBT is considered relapsed disease. Similarly progression to invasive UC tumors (T2-T4) at any time point is also considered relapsed disease and patients will not continue on dovitinib therapy.

#### **7.10.7.2 Urine Cytology**

All patients must have standard of care urine cytology obtained within 42 days prior to study registration. All patients will be re-evaluated for response by standard of care urine cytology obtained every 3 months  $\pm$  7 days (e.g. 3 month, 6 month, 9 month, 12 month) during the first year of follow-up. In the absence of recurrence at 1-year from study registration, additional urine cytology assessments are at the treating physician's discretion.

#### **7.10.7.3 Urine Fluorescent In-Situ Hybridization**

Testing of urine by fluorescent in-situ hybridization (FISH) for recurrence is not required at any time point as part of this study. The treating urologist may order commercial urine FISH testing (i.e. Urovysion®) at their own discretion.

### **7.10.8 Radiographic Evaluations**

#### **7.10.8.1 Abdomen and Pelvis CT scan**

All patients will have an abdomen and pelvis CT scan performed within 28 days prior to study registration. Subsequent scans while on study and in follow-up are at the treating physician's discretion.

### **7.10.8.2 Chest x-ray or Chest CT scan**

All patients will have a chest x-ray performed within 28 days prior to study registration. A chest CT may be substituted for the required chest x-ray provided it is also performed within 28 days prior to study registration. Subsequent x-rays and CT scans while on study and in follow-up are at the treating physician's discretion.

### **7.10.9 Cardiac Evaluations**

#### **7.10.9.1 Left Ventricular Ejection Fraction**

All patients will have left ventricular ejection fraction assessed within 28 days prior to study registration by either a 2-D echocardiogram or MUGA scan. Additional evaluations of left ventricular ejection fraction will be performed, as clinically indicated and at End of Treatment.

#### **7.10.9.2 Electrocardiogram**

All patients will have cardiac dysrhythmias and prior ischemic history assessed by 12-lead electrocardiogram within 28 days prior to study registration, at Cycle 1 Day 12 and Day 26, as clinically indicated in subsequent on-treatment cycles, and at End of Treatment.

### **7.10.10 Correlative Studies**

#### **7.10.10.1 Plasma FGFR3 Mutation Status**

Presence of FGFR3 mutation within circulating plasma will be assessed at baseline by the IUSCC TVC. Peripheral blood for plasma isolation will be obtained at Cycle 1 Day 1.

Plasma free RNA will be isolated utilizing a standard commercially available RNA extraction kit (i.e. QiaAmp™ Circulating Nucleic Acid Purification Kit). As the quantity of circulating free plasma RNA is expected to be low (picogram to nanogram range), FGFR3 mutations within circulating free plasma RNA will be assessed utilizing PCR-amplification of the target regions and sequencing. Refer to SPM for collection and shipping guidelines.

#### **7.10.10.2 Urine FGFR3 Mutation Status**

Presence of FGFR3 mutation within exfoliated urine tumor cells will be assessed at Cycle 1 Day 1 by the CLIA-certified Molecular Pathology and Translational Research Laboratory at the Dartmouth Hitchcock Medical Center. A 30 ml urine sample will be obtained from each patient at Cycle 1 Day 1 (this sample is separate from the standard of care urine cytology sample). Presence of FGFR3 mutations (see Table 1-2) within patient urine will be assessed by massively parallel sequencing of exons 7, 10, and 15 utilizing the Ion Torrent PGM instrument.

Refer to SPM for collection, processing and shipping guidelines.

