## 3.3 Exploratory Objectives

- To characterize concordance rates between UC patient detected tumor, urine, and circulating free plasma FGFR3 mutations.
- To characterize associations between pre-treatment germline (as assessed by PBMC extracted DNA) FGFR SNPs and post-treatment 6-month complete response rate and 1-year relapse free survival rate in patients treated with dovitinib.
- To characterize associations between pre-treatment germline (as assessed by PBMC extracted DNA) VEGFR SNPs and post-treatment 6-month complete response rate and 1-year relapse free survival rate in patients treated with dovitinib.

- To characterize VEGFR over-expression status within tumor tissue
- To characterize pre- and post-treatment bladder tumor FGFR and VEGFR pathway phosphorylation changes as assessed by bladder tumor tissue immunohistochemistry.
- To characterize post-treatment bladder tissue dovitinib concentrations.
- To characterize associations between post-treatment hypertension, 6-month complete response rate and 1-year relapse free survival rate in patients treated with dovitinib.

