## 5.2 Exclusion Criteria

Patients eligible for this study **must not meet any** of the following criteria:

1. Patients with muscle-invasive (i.e. T2, T3, T4), locally advanced non-resectable, or metastatic urothelial carcinoma as assessed on baseline radiographic imaging obtained within 28 days prior to study registration. The required radiographic imaging includes:
  - a. Abdomen/Pelvis – CT scan
  - b. Chest – chest x-ray or CT scan
2. Patients with concurrent upper urinary tract (i.e. ureter, renal pelvis) non-invasive urothelial carcinoma.

3. Patients with another primary malignancy within 3 years prior to starting study drug, with the exception of adequately treated in-situ carcinoma of the uterine cervix, clinically localized prostate cancer, biochemically relapsed non-metastatic prostate cancer (i.e. PSA only disease), or skin cancer (such as basal cell carcinoma, squamous cell carcinoma, or non-melanomatous skin cancer)
4. Patients who have received the last administration of an anticancer therapy including chemotherapy, immunotherapy, and monoclonal antibodies  $\leq$  4 weeks prior to starting study drug, or who have not recovered from the side effects of such therapy
5. Patients who have received targeted prior VEGFR or FGFR-targeted agents (i.e. sunitinib, pazopanib, sorafenib, bevacizumab, axitinib, etc.).
6. Patients who have had radiotherapy  $\leq$  4 weeks prior to starting study drug, or who have not recovered from radiotherapy toxicities
7. Patients who have undergone major surgery (e.g. intra-thoracic, intra-abdominal or intra-pelvic), open biopsy or significant traumatic injury  $\leq$  4 weeks prior to starting study drug, or patients who have had minor procedures (i.e. TURBT), percutaneous biopsies or placement of vascular access device  $\leq$  1 week prior to starting study drug, or who have not recovered from side effects of such procedure or injury
8. Patients with any of the following concurrent severe and/or uncontrolled medical conditions which could compromise participation in the study:
  - Impaired cardiac function or clinically significant cardiac diseases, including any of the following:
    - a. History or presence of serious uncontrolled ventricular arrhythmias
    - b. Clinically significant resting bradycardia

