- g. Archived pre-treatment tissue samples for study correlates will be collected from enrolled eligible patients. Blood and urine samples for study correlates will be collected at Cycle 1 Day 1 from enrolled eligible patients. The correlative analyses will be completed in batch groupings at study completion. Refer to SPM for collection, processing and shipping guidelines.
- h. Tissue for dovitinib PK analysis will be collected at the initial post-treatment cystoscopy with TURBT performed 3 months +/- 7 days after starting dovitinib therapy. Refer to SPM for collection, processing and shipping guidelines.
- i. Unstained slides are to be submitted from the pre-treatment TURBT specimen and from the post-treatment cystoscopy with TURBT performed 3 months +/- 7 days after starting dovitinib therapy. Refer to SPM for collection and shipping guidelines.

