## **7.2 Biomarkers**

All patients will be required to have bladder tumor FGFR3 mutation and over-expression status determined from a TURBT sample obtained within 42 days of registration. All other biomarker analyses will be exploratory in nature and do not need to be performed as part of study screening or eligibility assessments.

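### Fluids for FGFR3 concordance are drawn after the TURBT that supplies the tumor result, with no record of residual tumor, so fluid-negative pairs cannot be interpreted and the planned gamma can hide them

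*Combined protocol and SAP*

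**What the plan says.** The exploratory objective in Section 3.3 reads "To characterize concordance rates between UC patient detected tumor, urine, and circulating free plasma FGFR3 mutations".

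**Tumor result.** Section 7.2 requires FGFR3 status to be "determined from a TURBT sample obtained within 42 days of registration". Section 7.10.6.1 adds that slides from the "TURBT sample that was obtained within 42 days of registration will be submitted to two different laboratories prior to registration".

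**Fluid results.** For plasma, Section 7.10.10.1 says "Peripheral blood for plasma isolation will be obtained at Cycle 1 Day 1". For urine, Section 7.10.10.2 says "A 30 ml urine sample will be obtained from each patient at Cycle 1 Day 1". A footnote to Table 7-1 agrees: "Blood and urine samples for study correlates will be collected at Cycle 1 Day 1 from enrolled eligible patients". No fluid sample for FGFR3 is scheduled before the TURBT.

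**Interval.** Exclusion 7 in Section 5.2 covers "patients who have had minor procedures (i.e. TURBT), percutaneous biopsies or placement of vascular access device" if done no more than "1 week prior to starting study drug, or who have not recovered from side effects of such procedure or injury". Inclusion 1 allows the TURBT up to 42 days before registration, and Section 7.3 requires treatment to begin within 5 working days of registration. Section 7.1 gives assessments a general ±3-day window.

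**Residual tumor.** Section 7.10.7.1 judges the baseline TURBT adequate if at least one biopsy contains muscularis propria. The baseline list in Section 7.5 records tumor stage but not completeness of resection.

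**Analysis.** Section 10.2.6 forms each correlative set from all patients with evaluable data. Section 10.7.1 summarizes the tumor, urine and plasma comparison by Goodman-Kruskal gamma and calls all exploratory objectives hypothesis generating.

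**The concern.** A concordance analysis assumes that the specimens describe the same tumor in the same state. Here the reference specimen is obtained by resecting tumor, and the fluids are taken afterwards. Section 7.10.10.2 looks for the mutation in tumor cells shed into urine, so the signal depends on tumor being present. Section 7.10.10.1 already expects very little plasma RNA.

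Take two patients with an S249C tumor and a negative urine at Cycle 1 Day 1. In one the tumor was completely resected three weeks before, and the urine result is correct. In the other the tumor is still there, and the assay missed it. Both fall in the same tumor-positive/urine-negative cell, and no planned variable separates them.

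Section 1.2.3 presents this work as a search for more accessible ways to characterize tumor genomic material. The risk is a wrong conclusion about the fluids, in either direction. Low percent agreement could be read as a poor assay when the tumor had simply been removed, and a gamma of 1.00 could be read as full agreement when many mutations were missed. Only 10 mutation-positive patients are guaranteed, so with 10 each such pair moves positive agreement by 1/10, or 10 percentage points.

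**Working it through.** The documents state no expected concordance or precision for this objective, so there is no planned figure to reproduce. Two checks follow.

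**1. Interval from TURBT to sample**

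- Shortest: Exclusion 7 rules out a TURBT 7 days or less before first dose, so the gap is more than 7 days.
- Longest: 42 days to registration plus 5 working days (about 7 calendar days) = about 49 days.
- If the ±3-day window applies to the Cycle 1 Day 1 draw: more than 7 − 3 = 4 days, up to about 49 + 3 = 52 days.

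Very short gaps are unlikely, because the FGFR3 results take 5 to 7 days and must precede registration (Sections 7.10.6.1 and 7.10.6.2).

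**2. What lost fluid signal does to each statistic**

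Let *a* = tumor+/fluid+, *b* = tumor+/fluid−, *c* = tumor−/fluid+, *d* = tumor−/fluid−, and *n* = their sum.

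- Positive agreement = a/(a+b)
- Negative agreement = d/(c+d)
- Overall agreement = (a+d)/n
- Gamma in a 2×2 table = (ad − bc)/(ad + bc)

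From the documents: n = 20, with a minimum of 10 mutation-positive patients (Section 5.1). Assumed: exactly 10 positive, with fluid sensitivity and specificity against the tumor result as shown. The documents give neither.

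| Specificity | Sensitivity | a, b, c, d (expected) | Overall agreement | Gamma |
|---|---|---|---|---|
| 1.00 | 0.9 | 9, 1, 0, 10 | 0.95 | 1.00 |
| 1.00 | 0.5 | 5, 5, 0, 10 | 0.75 | 1.00 |
| 1.00 | 0.3 | 3, 7, 0, 10 | 0.65 | 1.00 |
| 0.95 | 0.9 | 9, 1, 0.5, 9.5 | 0.925 | 0.988 |
| 0.95 | 0.5 | 5, 5, 0.5, 9.5 | 0.725 | 0.900 |
| 0.95 | 0.3 | 3, 7, 0.5, 9.5 | 0.625 | 0.781 |
| 0.90 | 0.9 | 9, 1, 1, 9 | 0.90 | 0.976 |
| 0.90 | 0.3 | 3, 7, 1, 9 | 0.60 | 0.588 |

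Positive agreement equals the sensitivity column. For the second row, overall agreement = (5 + 10)/20 = 0.75 and gamma = (50 − 0)/(50 + 0) = 1.00. When c = 0, the product bc is zero whatever b is, so gamma cannot register missed mutations. It falls only if some patients are positive in fluid but not in tumor. If all 20 patients were mutation-positive, c = d = 0 and gamma would be undefined; Section 5.1 sets a minimum of 10 and no maximum.

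**Illustration of resection's effect on positive agreement.** Suppose a fraction *f* is completely resected, sensitivity is 0.80 with tumor in place and *s* after complete resection. Then positive agreement = (1 − f) × 0.80 + f × s. All three inputs are assumptions.

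| f | s = 0.10 | s = 0.30 |
|---|---|---|
| 0.3 | 0.56 + 0.03 = 0.59 | 0.56 + 0.09 = 0.65 |
| 0.5 | 0.40 + 0.05 = 0.45 | 0.40 + 0.15 = 0.55 |
| 0.7 | 0.24 + 0.07 = 0.31 | 0.24 + 0.21 = 0.45 |

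Against 0.80, the loss runs from 15 to 49 points. The width of that range shows a possible direction, not a size.

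**The case against.** A reader might infer that the TURBT removed the tumor and that the reported concordance is therefore biased downward. The documents do not support that, for two reasons. First, the baseline TURBT is a staging procedure. Complete resection is not required, and Section 7.10.6.1 describes patients with several biopsy sites, including separate foci of carcinoma in situ. How many patients are tumor-free at Cycle 1 Day 1 cannot be known. Second, the planned summary is gamma, which need not fall at all. Both objections stand, and they limit the claim to a probable effect on percent agreement.

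It can also be said that Cycle 1 Day 1 is a legitimate pre-treatment baseline, that Section 1.2.3 calls the fluid work purely exploratory, and that nothing states that urine or plasma is meant to replace tumor genotyping. This is fair, and it keeps the importance low. Section 10.1 does allow further exploratory analyses, and the TURBT-to-sample interval is probably derivable, since Table 7-1 marks TURBT as entered in the database. Neither supplies completeness of resection, which operative reports may not allow to be recovered reliably afterwards.

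The behavior of gamma does not rescue the plan. The objective names concordance rates, and gamma is a measure of association that can equal 1.00 when most mutations were missed in the fluid.

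**Conclusion.** The point holds in a limited form. The sampling order and the range of intervals follow directly from the documents, as does the absence of any record of residual tumor. A tumor-positive/fluid-negative pair is therefore ambiguous between resection and assay failure.

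That resection lowers positive and overall percent agreement is probable, on the premise that less tumor means less signal in the fluids. Its size cannot be derived; the figures above rest on assumed sensitivity, specificity and resection rates. For gamma, no downward bias can be asserted: with no fluid-only positives it stays at 1.00 and conceals the problem.

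The consequence is confined to an exploratory objective. Eligibility, the primary and secondary endpoints and safety are untouched.

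**What to change.** 1. Add one eCRF item, completed from the operative report of the staging TURBT: resection complete or incomplete, and whether residual tumor is known. Collect it prospectively.
2. In Section 10.7.1, report positive, negative and overall percent agreement with confidence intervals, separately for urine and plasma, in place of gamma or alongside it.
3. Show these for all patients, and split by residual-tumor status and by days from TURBT to sample.
4. Label the all-patient figure *post-resection detection* rather than concordance.

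The cost is one eCRF field and a few lines of analysis text, with no extra sample. The subgroups will be small and can only be described: if 30% to 70% of 10 mutation-positive patients were completely resected, 3 to 7 would remain with residual tumor, and a result of 4 of 5 has an exact 95% interval of roughly 28% to 99%.

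For that reason I would not make the residual-tumor subset the main analysis. Nor would I move sampling before TURBT for only some patients, which would mix two sampling conditions within 20 patients. It would also mean sampling before FGFR3 status is known: at the 40% prevalence in Section 10.8, about 1/0.40 = 2.5 patients for each one enrolled.
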